## 2.5. Randomization and Blinding

Randomization will be stratified by the following factors established at screening:

- IMDC prognostic score (1-2 risk factors [intermediate] vs 3-6 risk factors [poor])
- Region ([US or Canada or Europe or Australia or New Zealand] vs [Latin America or Asia])

The IMDC risk factors are (Heng et al 2009):

- KPS < 80%
- Less than 1 year from initial RCC diagnosis (including original localized disease if applicable) to systemic treatment
- Hemoglobin (g/L) < lower limit of normal (LLN)
- Corrected calcium (mg/dL) > 10 mg/dL
- Absolute neutrophil count (ANC) (G/L) > upper limit of normal (ULN)
- Platelet count ( $10^9/L$ ) > ULN

This is a double-blinded study. The cabozantinib-matched placebo will be given in combination with nivolumab and ipilimumab in the control arm to blind (mask) study treatment. The

assignment of study treatment will be unknown to the subjects, Investigators, study centers, Sponsor, and any clinical research organization (CRO) affiliated with the study other than those authorized to access treatment assignment for regulatory safety reporting and submission processes (see Protocol Section 8.2.2), Interactive Voice/Web Response System (IxRS) system administration, and drug supply management.

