#### 7.1.5. Primary Analysis

The timing of this analysis is event-driven and will be conducted after at least 249 events have been observed in the PITT population (the first 550 randomized subjects; see [Section 4.8.1](#)). It is designed to include progression events as determined by the BIRC per RECIST 1.1 or death whichever occurs earlier. Clinical deterioration determined by the Investigator will not be considered as progression events. If more than 249 events are included in the data cut off for the first 550 subjects, the primary analysis of PFS will include the first 249 events; supportive analysis including all PFS events in this population will also be provided. An additional supportive analysis of all PFS events in the first 440 randomized subjects through the data cutoff will be performed.

The hypothesis testing between experimental arm compared to the control arm will be performed using the stratified log-rank test with  $\alpha=0.05$  level of significance. The stratification factors are as described in [Section 2.5](#), and the values used for analysis will be those recorded in the IxRS.

The median duration of PFS along with the associated 95% CI for each study treatment arm will be estimated using the Kaplan-Meier method. The stratified HR and its 95% CI will be estimated using a Cox proportional-hazard model with treatment group as the independent variable using the same stratification factors as were used for the log-rank test.

If the p-value for the stratified log-rank test is less than the critical value for rejecting the null hypothesis and the HR ( $\lambda_{\text{cabozantinib} + \text{nivolumab} + \text{ipilimumab}} / \lambda_{\text{placebo} + \text{nivolumab} + \text{ipilimumab}}$ ) is  $< 1$ , the null hypothesis of no difference between the two study treatment arms will be rejected and it will be inferred that duration of PFS is greater in the experimental arm compared to the control arm.

The unstratified versions of all the above analyses will also be conducted.

A summary of concordance between the IRC and Investigator determinations of radiographic progressive disease per RECIST 1.1 (rPD) status, and rPD dates will also be provided.

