### 7.5.1. Objective Response Rate (ORR) by BIRC

For each subject, best overall response (BOR) is defined as the best tumor assessment category as determined per RECIST 1.1 by BIRC that occurs through the first overall time point response of PD and prior to any of the censoring events defined for the primary analysis of PFS as described in [Section 7.1](#). Tumor assessment categories are ranked as: confirmed CR, PR, SD, progressive disease (PD) and not evaluable (NE). To be classified as confirmed CR or confirmed PR, confirmation must have occurred on a subsequent visit that is  $\geq 28$  days after the response was first observed. To be classified as SD, at least one overall time point response of SD must be documented  $\geq 56$  days after randomization. The ORR is defined as the proportion of subjects with a best response (BOR) of confirmed CR or confirmed PR.

Descriptive testing for ORR will be performed using an unstratified two-sided chi-squared test at 5% level of significance. If a sufficient number of responders are observed, analysis using the

Cochran-Mantel-Haenszel method to adjust for the stratification factors (see [Section 2.5](#)) will be generated.

Point estimates of ORR for each study treatment arm, the difference in ORR between the study treatment arms, and associated  $(1-\alpha)$  % confidence intervals will be provided. The odds ratio and associated  $(1-\alpha)$  % confidence intervals will also be presented. The 2-sided CIs for the point estimate of ORR will be calculated using the Clopper Pearson's method. The 2-sided CIs for the difference in ORR between the two study treatment arms and for the odds ratio will be calculated using asymptotic methods. All summaries for ORR will be provided for the ITT and PITT populations.

Time to objective response is an arithmetic summary amongst those with an objective response and is defined as time from randomization to the first CR or PR that is subsequently confirmed. Time to objective response will be summarized with descriptive statistics.

Waterfall plots displaying maximum percent tumor reduction since baseline in target lesions will be generated for tumor assessment data per BIRC.

These plots will include subjects with a tumor assessment at baseline and at least one post-baseline visit. For each subject, data on or after the progression/censoring date of the respective PFS analyses described in [Section 7.1](#) will be excluded from the waterfall plots.

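### The stated ORR test ignores the randomization strata, the stratified analysis hangs on an undefined condition, and the interval method for the treatment comparison is not specified

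*SAP*

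**What the plan says.** SAP 2.5: "Randomization will be stratified by the following factors established at screening". The factors are IMDC score (intermediate or poor) and region (two groups), which makes four strata.

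SAP 7.5.1 (ORR by BIRC): "Descriptive testing for ORR will be performed using an unstratified two-sided chi-squared test at 5% level of significance". The next sentence makes the adjusted analysis conditional: "If a sufficient number of responders are observed, analysis using the" "Cochran-Mantel-Haenszel method to adjust for the stratification factors" is then to be generated. On intervals, the section says for each arm "The 2-sided CIs for the point estimate of ORR will be calculated using the Clopper Pearson's method", and for the comparison "The 2-sided CIs for the difference in ORR between the two study treatment arms and for the odds ratio will be calculated using asymptotic methods". SAP 7.5.2 carries the same methods to ORR by Investigator.

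SAP 7.1.5 (PFS): "The hypothesis testing between experimental arm compared to the control arm will be performed using the stratified log-rank test". It specifies the IxRS stratum values and a Cox model with the same strata, and adds unstratified versions of everything. SAP 7.2.3 applies the PFS methods to OS.

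Protocol 9.3 and SAP 7.3 place ORR outside the PFS-OS hierarchy. Its p-value is descriptive.

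**The concern.** When randomization is stratified by a factor that predicts response, an analysis that ignores the factor counts between-stratum variation as noise. The test becomes slightly conservative and the interval for the difference slightly too wide. The SAP accepts this logic for PFS and OS and reverses the order for ORR. Exploratory status does not explain the reversal, because the exploratory quality-of-life mixed models in SAP 7.5.9 include the randomization strata as fixed effects.

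Three things are left open:
- what number of responders triggers the CMH analysis, so that the decision falls after responses are known;
- whether the intervals for the difference and odds ratio are stratified;
- whether CMH uses IxRS or CRF values. SAP 7.1.5 fixes IxRS for PFS, while SAP 7.6 defines subgroups largely from the CRF.

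At stake are a little precision and a fully specified ORR result.

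**Working it through.** The documents give no sample size or power for ORR, so there is no design figure to reproduce on this point.

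**Inputs from the documents**
- N = 840 (ITT) or 550 (PITT), randomized 1:1.
- Control ORR 42%: the nivolumab plus ipilimumab result in intermediate- and poor-risk patients cited in the protocol synopsis and Section 1.5.
- IMDC mix: Protocol 1.6 reports 27 intermediate and 8 poor in the triplet arm of an earlier trial. 27/35 = 77%, used here as an assumed share w.

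**Assumptions not in the documents**
- ORR higher by 10 points on the experimental arm in every stratum (52% overall).
- A gap g of 0 to 30 points in ORR between the IMDC groups.
- Strata balanced between arms.

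**Will the CMH analysis be triggered?** Expected responders in 840: 0.42 × 840 = 353 with no effect, and 0.47 × 840 = 395 with a 10-point effect. In 550: 231 and 259. Any reasonable overall threshold would be met.

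**Variance of the ORR difference.** The unstratified variance is proportional to 0.42 × 0.58 + 0.52 × 0.48 = 0.2436 + 0.2496 = 0.4932. Stratifying removes w(1 − w)g² = 0.77 × 0.23 × g² = 0.1771g² from each arm. The proportional reduction is therefore 2 × 0.1771g² / 0.4932 = 0.718g².

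**Unstratified reference at N = 840.** SE = √(0.4932/420) = 0.0343, so the 95% half-width is 1.96 × 0.0343 = 6.72 points. The expected z is 0.10/√(0.47 × 0.53 × 4/840) = 2.90, and the chance of p < 0.05 is Φ(2.90 − 1.96) = 82.7%.

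**Size of the unstratified test under no effect.** 2[1 − Φ(1.96 × √(0.2436/(0.2436 − 0.1771g²)))].

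| Assumed IMDC gap | Control ORR, intermediate / poor | Variance reduction | Stratified half-width (unstratified 6.72) | Chance of p < 0.05 with CMH (unstratified 82.7%) | True size of unstratified 5% test |
|---|---|---|---|---|---|
| 0 points | 42.0% / 42.0% | 0% | 6.72 | 82.7% | 5.0% |
| 10 points | 44.3% / 34.3% | 0.7% | 6.69 | 83.0% | 4.9% |
| 20 points | 46.6% / 26.6% | 2.9% | 6.62 | 83.8% | 4.7% |
| 30 points | 48.9% / 18.9% | 6.5% | 6.50 | 85.1% | 4.3% |

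At N = 550 the chance of p < 0.05 goes from 65.2% to at most 68.0% over the same range.

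**Adding region.** With an assumed 65:35 region split and a 15-point region gap on top of the 30-point IMDC gap, the reduction is 6.5% + 2 × 0.65 × 0.35 × 0.15² / 0.4932 = 6.5% + 2.1%, or 8.5% before rounding of the parts (85.9% at N = 840).

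**The case against.** The strongest reply is that both analyses are already planned. The CMH analysis is in the next sentence, and with 350 or more expected responders it will almost certainly be produced. PFS and OS also report both forms, so only the order and the condition differ. This largely stands. A reader might infer that the plan gives up stratification for ORR; the text does not support that. It only fails to commit to it.

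A reader might also infer that the intervals for the difference and odds ratio are unstratified. SAP 7.5.1 says only that they "will be calculated using asymptotic methods", and Mantel-Haenszel intervals are asymptotic too. The defect is missing specification.

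The precision argument covers the test and the risk difference. It does not carry over to the odds ratio: a stratified odds ratio is a conditional quantity, not a sharper estimate of the marginal one, and the marginal one is a legitimate summary.

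A total responder count does not prove that every stratum is well filled. The documents give no region split or size for the smallest IMDC-by-region cell. That justifies some fallback, but a stated one.

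Finally, ORR is descriptive, has no alpha or power target, and the unstratified test is conservative. This stands in full and sets the weight of the point.

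**Conclusion.** The point holds as a low-cost improvement in method and specification. The lead ORR test does not use the strata the trial randomizes by, the trigger for the stratified analysis is undefined, and the interval method for the comparison is incomplete.

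The size is small: about 0% to 3% of the variance of the ORR difference for IMDC gaps up to 20 points, 6.5% at 30 points, and 8.5% with a large region gap added. At 20 points the half-width moves from 6.72 to 6.62 points. These figures rest on assumed response rates by stratum. The protocol supports IMDC risk as prognostic for survival (Section 1.1) but gives no response gap. There is no inflation of false positives, and neither the PFS nor the OS conclusion is affected.

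**What to change.** In SAP 7.5.1, and through it 7.5.2:
- Make CMH, stratified by IMDC group and region as recorded in IxRS, the lead ORR test.
- Report the Mantel-Haenszel common risk difference with a named stratified interval. Report the common odds ratio with its interval, labelled as stratum-adjusted.
- Replace the undefined responder condition with a stated rule for sparse strata, fixed before unblinding, for example collapsing over region if a stratum falls below a set count.
- Keep the unstratified chi-squared test and the marginal difference and odds ratio as supportive, and the Clopper-Pearson intervals for each arm as they are.

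The cost is SAP wording and standard SAS output. No new data, subjects or protocol amendment are needed.

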#### 7.1.4. Conventions for Analysis

Only adequate tumor assessments (ATAs) will be considered in the determination of radiographic progression and censoring dates. For the purpose of this study, an ATA is defined as one that results in a time point assignment of complete response (CR), partial response (PR), stable disease (SD; non-CR, non-PD), or progression, or not applicable (NA). Note that NA is assigned when a subject does not have any evidence of measurable or non-measurable disease.

The recorded date of radiographic progression is the date of the tumor assessment visit at which progression is declared. If multiple scan dates are associated with a tumor assessment visit, the earliest scan date within the set will be chosen as the progression date.

General censoring rules for the primary analysis of PFS are provided in [Table 9](#) (analysis ID PFS-EP-1).

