**Table 8: Event and Censoring Rules for Primary and Sensitivity Analyses**

Estimand	Primary		Primary		Primary	
Analysis type	Primary		Sensitivity		Sensitivity	
Analysis purpose	Primary		Evaluate assessment time bias		Evaluate assessor bias	
Analysis ID	PFS-EP-1		PFS-EP-2		PFS-EP-3	
Analysis name	rPFS per BIRC		Uniform dates		rPFS per Investigator	
Estimand endpoint	Radiographic PD		Radiographic PD		Radiographic PD	
Population	PITT		PITT		PITT	
Situation	Outcome	Date of Outcome	Outcome	Date of Outcome	Outcome	Date of Outcome
Radiographic PD per RECIST 1.1 per BIRC	event	date of recorded PD	event	date of scheduled visit (or next scheduled visit if between visits)	NA	NA
Radiographic PD per RECIST 1.1 per Investigator	NA	NA	NA	NA	event	date of recorded PD
Death	event	date of death	event	date of death	event	date of death
Intercurrent events (excluding those with Treatment Policy strategy for all estimands)						
Clinical deterioration	NA	NA	NA	NA	NA	NA
Systemic NPACT (medications)	censored	date of last ATA* before first initiation of therapy	censored	date of last ATA* before first initiation of therapy	censored	date of last ATA* before first initiation of therapy
Local NPACT (medications)	NA	NA	NA	NA	NA	NA
Surgical resection of target tumor lesion(s)	censored	date of last ATA* before target lesion resection	censored	date of last ATA* before target lesion resection	censored	date of last ATA* before target lesion resection
Local radiation: to soft tissue for disease under study	censored	date of last ATA* before local radiation of soft tissue for disease under study	censored	date of last ATA* before local radiation of soft tissue for disease under study	censored	date of last ATA* before local radiation of soft tissue for disease under study
Missing data						
No baseline ATA	censored	date of rand.	censored	date of rand.	censored	date of rand.
≥ 2 consecutive missing scheduled ATA immediately prior to analysis event	censored	date of last ATA* before missing visits	censored	date of last ATA* before missing visits	censored	date of last ATA* before missing visits
Observation ongoing						
None of the above criteria for event or censoring	censored	date of last ATA*	censored	date of last ATA*	censored	date of last ATA*

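### The waterfall-plot cut-off in SAP 7.5.1 removes the very scan that sets the progression or censoring date, which contradicts that section's inclusion sentence and its best-response window (minor)

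*SAP*

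**What the plan says.** SAP 7.5.1 describes the figure as "Waterfall plots displaying maximum percent tumor reduction since baseline in target lesions will be generated for tumor assessment data per BIRC". Two sentences then decide what goes into it.

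- Inclusion: "These plots will include subjects with a tumor assessment at baseline and at least one post-baseline visit".
- Exclusion: "For each subject, data on or after the progression/censoring date of the respective PFS analyses described in" SAP Section 7.1 "will be excluded from the waterfall plots".

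The dates come from the PFS rules.

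- **Progression (SAP 7.1.4).** "The recorded date of radiographic progression is the date of the tumor assessment visit at which progression is declared". If a visit has several scan dates, "the earliest scan date within the set will be chosen as the progression date".
- **Censoring (SAP Table 8, column PFS-EP-1).** For systemic non-protocol therapy the date is the "date of last ATA* before first initiation of therapy". Target-lesion resection, soft-tissue radiation, missed assessments and ongoing follow-up are handled the same way: the date is that of the last relevant adequate tumor assessment (ATA), or randomization if there is no post-randomization ATA. SAP 7.1.4 points to Table 9 for these rules, but they stand in Table 8.

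The best overall response (BOR) definition, also in SAP 7.5.1, takes the best category "that occurs through the first overall time point response of PD" and before any PFS censoring event.

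**The concern.** Apart from deaths and patients censored at randomization, the cut-off date is the date of a scan. A rule that drops data dated *on* the cut-off therefore drops the scan that created it. That scan is valid: an ATA has an evaluable response by definition, and for the intervention-related censoring reasons it comes before the intervention that led to censoring.

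Three things follow.

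1. The inclusion sentence admits a patient with progression at the first scan, and the exclusion sentence leaves that patient with no data. The SAP does not say how such a patient is shown.
2. Depth of response can be cut short in patients who are still responding at their last scan.
3. The BOR table and the waterfall plot use different scans for the same patient. Someone with a BOR of PD can have no bar.

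At stake is the accuracy of the per-patient picture of tumor shrinkage and its agreement with the response table. No hypothesis test is involved.

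**Working it through.** The plan gives no figure for this plot, so there is nothing to reproduce. The check applies the rules to patient profiles and then estimates scale.

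**Step 1: apply the rule.** The scan days and changes below are invented for illustration. As written, a scan is kept if its date is before the cut-off. The alternative also keeps the scan that defines the cut-off.

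| Profile | Scans (day: % change) | Cut-off day | Best change as written | Best change if the defining scan is kept |
|---|---|---|---|---|
| PD at first scan | 64: +35 | 64 | no data | +35 |
| Response, then PD | 64: −35; 120: −45; 176: −20 | 176 | −45 | −45 |
| Still deepening, censored at last ATA | 64: −20; 120: −35; 176: −50 | 176 | −35 | −50 |
| One scan, then systemic therapy | 64: −10 | 64 | no data | −10 |
| Death between scans | 64: −10; 120: −15 | 200 (death) | −15 | −15 |

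The rule removes the defining scan in every profile except death. It alters the bar only when that scan was the nadir or the only post-baseline scan.

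**Step 2: compare with BOR.** The BOR window runs through the first PD time point and stops at the censoring *event* (for example, the start of new therapy), not at the date of the last ATA. It therefore keeps both the PD scan and the last ATA that the plot drops.

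**Step 3: patients with an event by the first scan.** Inputs:

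- PFS medians of 11.6 and 17.6 months, exponential (SAP 2.4).
- First scan at W10D1 ± 7 days (Protocol 5.7.6.1), taken as day 64.
- 30.4375 days per month (SAP 4), so 64 / 30.4375 = 2.10 months.
- 550 / 2 = 275 per arm in the PITT population.

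P(event by the first scan) = 1 − 2^(−2.10 / median):

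- Control: 1 − 2^(−2.10/11.6) = 11.8%, and 0.118 × 275 ≈ 32.
- Experimental: 1 − 2^(−2.10/17.6) = 7.9%, and 0.079 × 275 ≈ 22.

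Over a scan window of 56 to 70 days, control gives 10.4% to 12.8% (29 to 35 patients) and experimental 7.0% to 8.7% (19 to 24). Under these assumptions the counts are upper bounds for first-scan PD, because they include deaths.

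**Step 4: patients exposed through censoring.** At 249 events in 550, 550 − 249 = 301 (55%) have no event. This counts patients exposed to the rule, not changed bars. It also includes anyone censored at randomization, who has no such scan to lose.

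**Step 5: scans available to patients under long observation.** SAP 4.8.1 gives a minimum follow-up of 15.6 months in the first 550, or 15.6 × 30.4375 / 7 ≈ 68 weeks. The imaging schedule places seven scans by then (weeks 10, 18, 26, 34, 42, 50 and 62). A patient observed throughout keeps about six after losing the last. Patients censored early keep fewer, and the documents do not show how many there are.

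**The case against.** The strongest case against concerns size, not logic.

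- **Direction.** A reader might infer that the figure overstates shrinkage overall. The documents do not support that. Losing first-scan progressors removes some poor bars. Losing the last scan of a censored patient can only lower that patient's maximum reduction, leave it unchanged, or remove the bar. The effects can oppose each other, and no net figure can be derived.
- **The 55%.** A reader might take 301 of 550 as the number of wrong bars. It is not, for the reasons in Steps 1, 4 and 5.
- **Upward bars.** Under Protocol Appendix F, PD can come from new lesions or non-target progression while target lesions are stable or shrinking. The first-scan progressors lost would not all be upward bars. The difference between arms also assumes that the design medians hold.
- **Vanishing patients.** The inclusion sentence formally keeps first-scan progressors. What the text contains is a conflict between two sentences, with no instruction for a patient left without data.
- **Importance.** SAP 7.5 treats exploratory results as supportive, and no estimate or decision uses this plot. First-scan progressors remain visible in the BOR and ORR tables.

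All five points stand, and they limit the finding to a minor one. They do not remove it: the rule as stated discards valid scans, gives no reason for doing so, and disagrees with two other sentences in its own section.

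**Conclusion.** The rule is wrong as written, and the severity is minor. It follows from SAP 7.1.4, Table 8 and the exclusion sentence that the scan defining the progression or censoring date is dropped. First-scan progressors are left with no data, and some censored patients have a shortened or missing bar.

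For first-scan progression the scale is at most about 32 control and 22 experimental patients of 275 per arm. This rests on exponential PFS at the design medians and a scan at the nominal week 10. For censoring, up to 301 of 550 are exposed, but only those whose last ATA was the nadir or the sole post-baseline scan are affected, and that number cannot be obtained from the documents.

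Neither an overall overstatement of shrinkage nor a bias favoring one arm is established. The PFS and OS tests and the ORR do not depend on this rule.

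**What to change.** Define the cut-off by visit instead of by date. Suggested wording: *Data from tumor assessment visits after the visit that defines the progression/censoring date of the respective PFS analysis will be excluded from the waterfall plots; where that date is a death or randomization date, data after that date will be excluded.*

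This keeps every scan of the PD visit and the last ATA before censoring, in line with the inclusion sentence and the BOR window. Merely deleting *on or* is not quite enough. SAP 7.1.4 takes the earliest scan date of a visit with several dates, so target-lesion images taken later in the same PD visit would still be lost.

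The cost is one sentence in the SAP and a small change to the plotting program. SAP 4.8 already allows clarifications and minor corrections by addendum before final analyses. No other output changes.
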